## **1.5. Compliance**

This study will be conducted in compliance with this protocol, Good Clinical Practice (GCP), and all applicable regulatory requirements.

## **2. OBJECTIVES**

The primary objective of this study is:

- To evaluate the effect of filgotinib on testicular function as defined by the proportion of subjects with a  $\geq 50\%$  decrease from Baseline in sperm concentration at Week 13

The secondary objectives of this study include:

- To evaluate the effect of filgotinib on testicular function as defined by the proportion of subjects with a  $\geq 50\%$  decrease from Baseline in sperm concentration at Week 26
- To evaluate the effect of filgotinib on sperm total motility at Weeks 13 and 26
- To evaluate the effect of filgotinib on total sperm count at Weeks 13 and 26
- To evaluate the effect of filgotinib on the change from Baseline in sperm concentration at Weeks 13 and 26
- To evaluate the effect of filgotinib on ejaculate volume at Weeks 13 and 26
- To evaluate the effect of filgotinib on sperm morphology at Weeks 13 and 26

The exploratory objectives of this study include:

- To evaluate the reversibility of observed effects of filgotinib on testicular function in subjects who experience a  $\geq 50\%$  decrease in sperm concentration, and/or motility, and/or morphology

- To evaluate the effect of filgotinib on sex hormones, including luteinizing hormone (LH), follicle stimulating hormone (FSH), inhibin B, and total testosterone at Weeks 13 and 26
- To evaluate the safety and tolerability of filgotinib
- To characterize the plasma PK of filgotinib and its metabolite (GS-829845, formerly CCI [REDACTED])

### 3. STUDY DESIGN

This is a randomized, double-blind, placebo-controlled, Phase 2 study in adult males with active RA, PsA, AS or nrAxSpA who have had an inadequate response to prior arthritis therapy as outlined in the inclusion criteria, an adverse prognosis of their condition per the investigator and may benefit from treatment with a JAK inhibitor.

Up to 250 males between the ages of 21 and 65 years (inclusive) at the time of consent will be randomized to receive filgotinib 200 mg or placebo once daily for 13 weeks.

Randomization will be stratified according to the type of rheumatic condition (RA or Spondyloarthritis [PsA, AS, nrAxSpA]), by concurrent use of MTX (yes or no), and by sperm concentration measured at Screening (“Baseline”) according to the following strata:

[figure not shown]
- 15 to 25 million/mL
- > 25 to 50 million/mL
- > 50 million/mL

Male subjects with RA, PsA, AS or nrAxSpA who provide written informed consent will be screened to determine eligibility as per the inclusion and exclusion criteria (see Section 4.2 and 4.3, respectively).

The Screening period will be up to 45 days and may be extended in consultation with the Sponsor Medical Monitor. During the Screening period, subjects will provide 2 semen samples within a 14-day period as detailed in Section 6.11 (ie, the Screening (“Baseline”) sample).

The assessments to be performed at each visit are detailed in the study procedures table (Appendix 2). A schematic of the study design is provided below.

**Figure 3-1. Study Scheme**

\* Subjects on filgotinib who are non-responders at week 13 will switch to Standard of Care treatment

^At any visit, subjects who have a 50% decrease in sperm concentration and/or sperm motility and/or sperm morphology as compared to baseline, will enter a Monitoring Phase for evaluation of reversibility

#Subjects on filgotinib will discontinue study drug and start Standard of Care. Subjects on Standard of Care will continue treatment. All subjects will have semen evaluations every 13 weeks for up to 52 weeks or until Reversibility is met

[figure not shown]
There are 3 distinct parts to the study:

- 1) Double-blind Treatment Phase (Day 1 through Week 13 Study Visit)
- 2) Extension Phase (After Week 13 Study Visit and up to Week 156)
- 3) Monitoring Phase (up to 52 weeks)

After fulfilling all selection criteria, subjects will be randomized to filgotinib or placebo (1:1) at Day 1 and enter the Double-blind Treatment Phase. Based on the outcomes of the Week 13 assessments (ie, individual subject's response of the underlying rheumatic condition to the assigned treatment and/or the observed changes in sperm parameters during the double-blind treatment phase), subjects may enter the Extension or Monitoring Phase.

### 3.1. Double-blind Treatment Phase (Day 1 through Week 13 Study Visit)

Figure 3-2. Double-blind Treatment Phase – Week 13 Evaluation

[figure not shown]

During the Double-blind Treatment Phase, all subjects will receive blinded study drug for 13 weeks starting from the Day 1/Randomization Study Visit. Subjects will visit the clinical study center to be evaluated for clinical and laboratory assessments at Day 1, Week 2, Week 4, Week 8, and Week 13. At the Week 13 study visit, sperm parameters (see Semen collection and Analysis) will be evaluated to determine whether they meet any of the pre-specified decrease thresholds (see [Definition of Terms](#)). In addition, arthritis response status (Arthritis Non-responder vs Arthritis Responder, see [Definition of Terms](#)) will be determined. As soon as the Week 13 semen results are available to the investigator and have been evaluated, subjects are assigned to one of the following:

- Subjects whose semen parameters meet any of the pre-specified decrease thresholds, regardless of arthritis response status, will discontinue blinded study drug and enter the Monitoring Phase. These subjects will also have a safety follow-up visit 30 days after last study drug dose.
- Subjects who are arthritis Non-responders and whose sperm parameters do not meet any of the pre-specified decrease thresholds will discontinue blinded study drug and start Standard of Care treatment (see [Definition of Terms](#)) during the Extension Phase. These subjects will also have a safety follow-up visit 30 days after last study drug dose.
- Subjects who are Arthritis Responders and whose sperm parameters do not meet any of the pre-specified decrease thresholds will be unblinded by the IWRS system and enter the Extension Phase. Subjects on filgotinib will convert to open-label filgotinib and subjects receiving placebo will switch to Standard of Care treatment.

### 3.2. Extension Phase

**Figure 3-3. Extension Phase – Evaluation**

\*Open-label treatment with filgotinib or Standard of Care. Adjustment of background treatment with non-prohibited medication allowed at any time during the Extension Phase

In the Extension Phase, subjects will receive open-label treatment (filgotinib or Standard of Care) and have a study visit every 13 weeks that includes semen analysis. The first scheduled visit of the Extension Phase occurs at Week 26.

In case sperm parameters at any visit (including Week 156) meet any of the pre-specified decrease thresholds, subjects will enter the Monitoring Phase.

During the Extension phase, Standard of Care and background treatment concomitant to filgotinib may be optimized at the discretion of the investigator, taking into consideration the protocol restrictions.

[figure not shown]
In case a subject needs to be treated with a prohibited medication (see [Table 5-1](#)), for instance to control their rheumatic condition, the subject will discontinue the study and complete an Early Termination (ET) visit (including semen collection). For subjects on filgotinib, this will be followed by a safety follow-up visit 30 days after last study drug dose.

All subjects who did not enter the Monitoring Phase will continue the study until the Week 156 visit.

In the Extension Phase, subjects must have yearly Quantiferon® testing. Yearly TB testing begins 1 year from the screening TB test date. If yearly TB testing falls between study visits, the yearly TB testing should be performed at the visit prior to 1 year from the screening TB test date. Subjects with newly positive (converted) Quantiferon® (or centrally reported equivalent assay) TB test should be discontinued from the study. Subjects who were previously treated for TB with a complete and adequate course of therapy as per local Standard of Care and as verified by the investigator do not need to have yearly tests.

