Study Drug	Study drug is defined as blinded filgotinib or placebo during the Double-blind Treatment Phase and open-label filgotinib during the Extension Phase.
First unblinded interim analysis (IA1)	Unblinded Week 26 analysis to be performed after at least 200 evaluable subjects pooled across studies GS-US-418-4279 (GLPG0634-CL-228) and GLPG0634-CL-227 complete Week 13 and evaluable subjects from Study GLPG0634-CL-227 complete Week 26 or permanently discontinue from study drug. Referred to as 'Week 26 Analysis' in the SAP.
Second unblinded interim analysis (IA2)	Unblinded Week 26 analysis to be performed after all subjects reach Week 26 and all subjects with a $\geq 50\%$ decrease in sperm concentration, and/or motility, and/or morphology up to Week 26 enter the Monitoring Phase and either meet reversibility criteria or are followed off-treatment for 52 weeks, whichever occurs first. Referred to as 'Week 26 and Reversibility Analysis for Pre-specified Sperm Decreases Up to Week 26' in the SAP.

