### **3.7.2. Study Drug Discontinuation Considerations:**

The Sponsor Medical Leader or designee should be consulted prior to study drug discontinuation when medically feasible.

Study drug should be permanently discontinued in the following instances:

- Any opportunistic infection
- Any serious infection that requires parenteral/intravenous antimicrobial therapy or hospitalization, or any infection that meets serious adverse event (SAE) reporting criteria.
- Febrile neutropenia (temperature  $>38.3^{\circ}\text{C}$  or a sustained temperature of  $>38^{\circ}\text{C}$  for more than 1 hour) with absolute neutrophil count of  $<1,000/\text{mm}^3$
- Symptomatic anemia (eg, signs/symptoms including pallor, shortness of breath, new heart murmur, palpitations, lethargy, fatigue) with hemoglobin  $<7.5$  g/dL, or if transfusion is indicated regardless of hemoglobin value
- Complicated herpes zoster infection (with multi-dermatomal, disseminated, ophthalmic, or CNS involvement)
- Evidence of active Hepatitis C virus (HCV) during the study, as evidenced by HCV RNA positivity
- Evidence of active Hepatitis B virus (HBV) during the study, as evidenced by HBV deoxyribonucleic acid (DNA) positivity
- Any thromboembolic event that meets SAE reporting criteria

- Unacceptable toxicity, or toxicity that, in the judgment of the investigator, compromises the ability to continue study specific procedures or is considered to not be in the subject's best interest
- A  $\geq 50\%$  decrease from Baseline (based on the mean of 2 separate semen samples collected at the Screening Visit) in sperm concentration and/or motility and/or morphology
- Subject request to discontinue for any reason
- Subject noncompliance to the protocol
- Discontinuation of the study at the request of the Sponsor, a regulatory agency or an institutional review board or independent ethics committee (IRB/IEC)
- Subject's use of prohibited concurrent therapy will trigger study discontinuation; consultation should be made with the Sponsor Medical Leader or designee
- Subjects with newly positive (converted) QuantiFERON® TB test (or centrally reported equivalent assay) and/or any subject with active TB
- Any of the below described abnormal laboratory changes occurring at any one time, and confirmed by repeat testing ([Appendix 11](#)):
  - 2 sequential neutrophil counts  $<0.75 \times 10^9$  cells/L (750 neutrophils/mm^3)

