## **6.5. Extension Phase**

In the Extension Phase, subjects will receive open-label treatment (filgotinib or Standard of Care) and have a study visit every 13 weeks that includes semen analysis. The first scheduled visit of the Extension Phase occurs at Week 26.

In case sperm parameters at any visit (including Week 156) meet any of the pre-specified decrease thresholds, subjects will enter the Monitoring Phase.

During the Extension phase, Standard of Care and concomitant treatment may be optimized at the discretion of the investigator taking into consideration the protocol restrictions (see Section 5.3).

In case a subject needs to be treated with a prohibited medication to control their rheumatic condition (see [Table 5-1](#)), the subject will discontinue the study and complete an ET visit (including semen collection). For subjects on filgotinib, this will be followed by a safety follow-up visit 30 days after last study drug dose.

All subjects who did not enter the Monitoring Phase will continue the study until the Week 156 visit.

Subjects with newly positive (converted) QuantiFERON® [or centrally reported equivalent assay] TB test should be discontinued from study drug. Subjects who were previously treated for TB with a complete and adequate course of therapy as per local standard of care and as verified by the investigator do not need to have yearly QuantiFERON® tests. Subjects previously treated for TB should be screened at least yearly for signs and symptoms consistent with reactivation of TB. Any subject with active TB should be discontinued from the study.

Study assessments will be completed as specified in the Study Procedures Table ([Appendix 2](#)).

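### The protocol gives two consequences for TB-test conversion in the Extension Phase, leaving the study or stopping study drug, and does not say what applies to men on Standard of Care

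*Protocol*

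**What the plan says.** Yearly testing is set out in Protocol Section 3.2: "In the Extension Phase, subjects must have yearly Quantiferon® testing". The requirement is not limited to men on filgotinib; the only exemption is for subjects already adequately treated for TB. For a conversion, Section 3.2 says that a newly positive "TB test should be discontinued from the study".

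Section 6.5 covers the same phase and the same event and says "TB test should be discontinued from study drug". It then treats active disease separately: "Any subject with active TB should be discontinued from the study". Footnote c of the Extension Phase table in Appendix 2 makes the same split, and SAP Appendix 1 reproduces that footnote.

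Section 3.7.2 opens its list with "Study drug should be permanently discontinued in the following instances". Its TB item covers converters "or centrally reported equivalent assay) and/or any subject with active TB", so both events carry the one stated consequence, a permanent stop of study drug.

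Two other provisions fix what these words mean in practice. The Definition of Terms says: "Study drug is defined as blinded filgotinib or placebo during the Double-blind Treatment Phase and open-label filgotinib during the Extension Phase". Standard of Care is therefore not study drug. Section 3.2 also says: "All subjects who did not enter the Monitoring Phase will continue the study until the Week 156 visit".

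**The concern.** Stopping study drug and leaving the study are different actions in this protocol, with different follow-up. A site working from Section 3.2 and a site working from Section 6.5 or the procedures table could each follow the protocol and handle the same man differently. What is at stake is later data: the 13-weekly semen visits to Week 156, any later entry to the Monitoring Phase with its reversibility assessment, and long-term safety follow-up. The same event could also appear in the SAP disposition tables either as a study-drug discontinuation or as a study discontinuation, depending on the section followed.

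**Working it through.** No figure in the plan depends on this rule, so the check is a comparison of texts plus visit arithmetic.

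**Step 1. Consequence stated in each place.**

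| Place | TB-test conversion | Active TB |
|---|---|---|
| Protocol 3.2 | leave study | not addressed |
| Protocol 3.7.2 | stop study drug | stop study drug |
| Protocol 6.5 | stop study drug | leave study |
| Protocol Appendix 2, Extension Phase, footnote c | stop study drug | leave study |
| SAP Appendix 1, Extension Phase, footnote c | stop study drug | leave study |

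The direct conflict on conversion is Section 3.2 against Section 6.5 and footnote c. On active TB, Section 3.7.2 names only the drug stop, whereas 6.5 and footnote c name study exit.

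**Step 2. Is there a tie-breaker?** Section 7.6 says that the more conservative criteria apply where there is a discrepancy. That sentence sits in a paragraph ranking the Section 3.7 criteria over the general toxicity guidelines in Section 7.6. It does not rank Section 3.2 against Section 6.5.

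**Step 3. What each reading means for follow-up** (Sections 3.2, 6.7, 6.8; Appendix 2).

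| Extension Phase treatment | Leaves the study | Stops study drug, stays in the study |
|---|---|---|
| Open-label filgotinib | Early Termination (ET) visit and 30-day safety visit | 30-day safety visit, then 13-weekly visits to Week 156 |
| Standard of Care | ET visit | no drug to stop; 13-weekly visits to Week 156 unchanged |

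The ET visit includes semen collection unless samples were taken within the previous 2 weeks.

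**Step 4. Timing of the first yearly test.** Inputs: screening of up to 45 days (Section 3), and a test due at the visit before one year from the screening TB test (Section 3.2). The anniversary then falls as early as 365 − 45 = 320 days after Day 1. Week 39 is 39 × 7 = 273 days and Week 52 is 52 × 7 = 364 days. Since 273 < 320 < 364, the first test falls at Week 39.

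**Step 5. Semen visits at stake per man.** Remaining visits = (156 − week of conversion)/13.
- Found at Week 39: (156 − 39)/13 = 9.
- Found one year later, at Week 91: (156 − 91)/13 = 5.
- Found at Week 143: (156 − 143)/13 = 1.

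Outside the 45-day assumption, inclusion criterion 11 allows a prior result up to 60 days old to be reused. If that date counted as the screening test date, the anniversary could fall at 365 − (45 + 60) = 260 days. That is before the Week 39 visit, so the test would move to Week 26, with (156 − 26)/13 = 10 visits remaining. This is why the Week 26 endpoints are called essentially, rather than wholly, unaffected.

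**Step 6. Effect on planned analyses.** For men on open-label filgotinib, the note to SAP Table 3-4 cuts on-treatment semen data at the end of extension-phase dosing, or at last dose + 7 days. SAP Section 8 cuts extension-phase safety data at last dose + 30 days. Those summaries change little under either reading. For men on Standard of Care, data count up to the end of their extension phase, and both Standard of Care sequences appear in the Week 39 and later displays (SAP Section 6.5.2). For them, leaving the study removes data that would otherwise be summarized.

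**The case against.** The strongest reply is that little depends on this. The first yearly test normally comes well after Week 13, and the later displays are descriptive summaries by treatment sequence. Men who leave still have an ET visit. The Sponsor Medical Leader should be consulted before study drug is stopped, when medically feasible (Section 3.7.2), which should reduce variation between sites. The Amendment 2 rationale says that the study had already passed the analysis time points for its primary, secondary and exploratory endpoints, so few visits remain to benefit. All of this stands as a limit on size. It does not remove the contradiction, and the consultation rule does not reach men on Standard of Care, who have no study drug to stop.

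A second reply is that Section 3.7.2 is compatible with Section 3.2, because a man who leaves the study also stops drug, and other items on that list do refer to ending study participation. That is fair. Section 3.7.2 should not be read as limiting the consequence to a drug stop, nor as keeping study exit for active TB; only Section 6.5 and footnote c draw that line.

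A reader might also infer that all semen and adverse-event follow-up is lost under Section 3.2, or that sites are certain to diverge. The documents support neither: the ET visit remains (plus the 30-day safety visit for men on filgotinib), and actual site behavior is unknown.

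**Conclusion.** The contradiction holds and sits in current operative text. Section 3.2 ends study participation on conversion; Section 6.5 and footnote c stop study drug. The consequence of active TB also differs between Section 3.7.2 and those two places. The issue is minor in size and falls mainly on men on Standard of Care, for whom the readings are exit or no action. Up to 9 later semen visits per man are at stake if conversion is found at about Week 39, and fewer if later. That figure assumes a screening TB test within about 45 days of Day 1. The documents give no conversion rate; the number of men is probably small. A reader might infer a threat to the primary endpoint; the test timing rules that out. The exposure is in the Week 39 and later displays, later Monitoring Phase entry and reversibility, and long-term safety.

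**What to change.** Reconcile Protocol Sections 3.2, 3.7.2 and 6.5 and footnote c of the Extension Phase table in Appendix 2, so that one consequence is stated for TB-test conversion and one for active TB. State explicitly what each means for a subject on Standard of Care, and bring SAP Appendix 1 into line. Which rule is right is a clinical decision for the sponsor and is not addressed here.

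The change is to wording only, with no effect on sample size or analysis methods. It is not quite free, because Section 9.2.1 requires protocol modifications to go through IRB/IEC review before they are implemented; it could be carried with any other amendment. For conversions that have already occurred, the clinical study report could state by treatment sequence whether each man left the study or stopped study drug.

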### 3.3. Monitoring Phase (up to 52 weeks)

Figure 3-4. Monitoring Phase - Evaluation

\*Adjustment of background treatment with non-prohibited medication allowed at any time during the Monitoring Phase

Subjects whose sperm parameters meet any of the pre-specified decrease thresholds will switch to the Monitoring Phase immediately. Subjects on double-blinded treatment or open-label filgotinib who enter the Monitoring Phase will discontinue study drug and start Standard of Care. These subjects will also have a safety follow-up visit 30 days after last study drug dose. Subjects on Standard of Care will continue treatment.

All subjects who enter the Monitoring Phase will undergo semen evaluations every 13 weeks starting from their entry into the Monitoring Phase, for up to 52 weeks or until Reversibility (see [Definition of Terms](#)) is met, whichever is achieved first.

In case a subject needs to be treated with a prohibited medication (see [Table 5-1](#)), for instance to control their rheumatic condition, the subject will discontinue the study and complete an ET visit (including semen collection).

### 3.4. Semen Collection and analysis:

At each of the following time points, subjects will provide 2 separate semen samples collected within a 14-day period. Each semen sample must be collected with a  $\geq 48$  hours and  $\leq 7$  days ejaculation free period (Section [6.11](#)) at the following time points.

- Screening (Baseline)
- After the Double-blind Treatment Phase (Week 13 study visit)
- Every 13 weeks during the Extension Phase
- Every 13 weeks during the Monitoring Phase
- At the Early Termination Visit

In select cases where the semen sample with questioned value(s) is found to be non-assessable or invalid (eg, collection without adherence to ejaculation-free period; intercurrent illness or dehydration at time of collection; incomplete capture of semen sample; and/or sample processing or semen analysis that deviates from standardized procedure), a third semen sample, when indicated, must be collected within 14 days of the prior sample and with an ejaculation free period of  $\geq 48$  hours and  $\leq 7$  days. All decisions on retesting any semen/sperm parameters (ie, obtaining a third semen sample at any of the above time points) must be confirmed by the Sponsor Medical Leader or designee before the retest.

